## 1 PROTOCOL SYNOPSIS

- Product:** AT-1501 1.0, 2.0, 4.0 or 8.0 mg/kg for IV infusion
- Study Title:** A Phase 2a Open-Label, Multi-Center Study to Evaluate the Safety and Tolerability of Multiple Doses of AT-1501 in adults with ALS
- Centers:** This study will be performed at up to twelve centers in the United States and one site in Canada.
- Primary Objective:** To determine the safety and tolerability of IV administration of multiple doses of AT-1501 in adults with ALS.

### Exploratory Objectives:

- [REDACTED]
- [REDACTED]
- [REDACTED]
- [REDACTED]

### Study Design

This is a Phase 2a, multi-center, open label, multiple dose study of AT-1501, a humanized monoclonal antibody antagonist to CD40LG. Approximately 54 adults with ALS will be enrolled into the study in the United States at up to 12 ALS treatment sites.

Four ascending doses of AT-1501 (1.0 mg/kg; 2.0 mg/kg; 4.0 mg/kg and 8.0 mg/kg) will be administered as a 1-hour IV infusion to sequentially enrolling cohorts. The 1.0 mg/kg and 2.0 mg/kg cohorts will consist of 9 participants each and the 4.0 mg/kg and 8.0 mg/kg cohorts will consist of 18 participants each. The participants in each cohort will receive 6 bi-weekly (every other week) infusions of AT-1501 over an 11-week period.

This study consists of a 4 week screening period, an 11 week dosing period in which participants are dosed once every other week, and a 4 week follow-up period. On Day 1 eligible participants will receive their first 1-hour intravenous (IV) infusion of AT-1501 and will be observed for at least 2 hours post infusion before being released from the clinical site. They will return on Weeks 3, 5, 7, 9 and 11 for subsequent infusions and will remain at the clinical site for at least 2 hours for observation and assessments before being released. Participants will be called weekly between dosing visits (Weeks 2, 4, 6, 8, 10 and 12) by a member of the research team to record adverse events (AE) and changes in concomitant medications. Participants will be followed for an additional 4 weeks after their last dose to monitor for safety, with an end of study clinic visit occurring Week 15.

Each participant will be monitored for safety throughout the study. Safety will be assessed by evaluation of AEs, changes in safety laboratory parameters, physical examination including vital signs, ECGs and the Columbia Suicide Severity Rating Scale (C-SSRS). [REDACTED]

[REDACTED]

The dose limiting toxicity observation period to determine the safety of a dose level is defined as starting with administration of the first dose of AT-1501 to the first participant in a cohort through the administration of the second dose of AT-1501 in the 6th participant in that cohort (See 10.3 for Stopping Rules and Dose Limiting Toxicity).

The Data Monitoring Committee (DMC) will meet following the administration of 6 doses to a minimum of 33% of participants, in each cohort, (3 participants in cohorts 1 and 2 will have received 6 doses for a total of 18 doses, and 6 participants in cohorts 3 and 4 will have received 6 doses for a total of 36 doses) to review safety data and to make dose escalation recommendations to Anelixis.

**Target Population:** Adults with ALS who meet the inclusion/exclusion criteria.

[figure not shown]

**Safety:** Each participant will be monitored for safety throughout the study. Safety will be assessed by evaluation of AEs, changes in safety laboratory parameters (with special attention to platelet and coagulation values), physical examination including vital signs, ECGs and the C-SSRS.

## 2.1 Abbreviations and Definition of Terms

Abbreviation	Definition
AE	Adverse Event
ALS	Amyotrophic Lateral Sclerosis
ALSFRS-R	ALS Functional Rating Scale – Revised
ALT	Alanine aminotransferase (alanine transaminase)
AST	Aspartate aminotransferase (aspartate transaminase)
CD40LG	CD40 Ligand
CBC	Complete Blood Count
CRF	Case Report Form
CRO	Contract Research Organization
C-SSRS	Columbia Suicide Severity Rating Scale
CTCAE	Common Terminology Criteria for Adverse Events v 4.03
CV	Curriculum Vitae
ECG	Electrocardiogram
FAS	Full Analysis Set
GMP	Good Manufacturing Practice
ICH	International Conference of Harmonization
IRB	Institutional Review Board
ITT	Intent-to-Treat
IU	International unit
kg	kilogram
MedDRA	Medical Dictionary for Regulatory Activities
mL	milliliter
MR1	A hamster antibody targeted against murine CD40LG.
NHP	Non-human primate
PP	Per-Protocol
PT	MedDRA Preferred Term
SAE	Serious Adverse Event
SAP	Statistical Analysis Plan
Sec	Seconds
SDV	Source Data Verification
SOA	Schedule of Activities
SOC	MedDRA System Organ Class
SOP	Standard Operating Procedure
SPC	Summary of Product Characteristics
SVC	Slow Vital Capacity
TE	Thromboembolism
TEAE	Treatment-Emergent Adverse Event
WBC	White Blood Cell Count

All dimensional units are in standard SI units

### 3 INTRODUCTION

Amyotrophic Lateral Sclerosis (ALS) is a fatal, degenerative disorder of motor neurons that results in progressive wasting and paralysis of voluntary muscles. There is mounting evidence that the disease progression is mediated in part by immune activation. Prior research aimed at non-specific immunomodulatory therapies targeting the immune system broadly have not identified successful therapies for ALS. Antibodies blocking CD40LG have been shown to successfully reduce the activation of circulating lymphocytes, monocytes, macrophages, and other antigen presenting cells (see Section 0).

This multiple ascending dose protocol will study the safety, tolerability, [REDACTED] in adults with ALS.

A First-in-Human single ascending dose study with doses of 0.5 mg/kg; 1.0 mg/kg; 2.0 mg/kg; 4.0 mg/kg and 8 mg/kg was successfully carried out with no safety or tolerability concerns. The safety data and pharmacokinetics of this initial study is available in the Investigator's Brochure.

#### 3.1 Humanized Blocking Antibody to CD40LG

Preclinical testing in a murine model of ALS has demonstrated statistically significant slowing of the disease course in animals treated with MR1, a hamster antibody targeted against murine CD40LG. [Lincecum 2010]. Furthermore, analysis reveals decreased immune activation in treated animals, with less macrophage invasion of nerves in the periphery and less gliosis in the central nervous system. Based on this evidence, a humanized blocking antibody to CD40LG, AT-1501, was tested in healthy adults (0.5, 1.0, 2.0, 4.0 and 8.0 mg/kg) as well as adults with ALS in a single ascending dose study. (Three adults with ALS received 1.0 mg/kg.)

#### 3.2 Other Experiences with Drugs Targeting CD40LG

[REDACTED]

[REDACTED]

AT-1501 was designed to mitigate the risk of thrombotic events seen with an earlier anti-CD40LG antibody by introducing structural modifications that do not alter binding of AT-1501 to CD40LG

but reduce antibody dependent cellular cytotoxicity (ADCC), complement activation and platelet activation associated with Fcγ receptor binding [Saxena 2016]. The preclinical data support a low risk of thromboembolic (TE) events in susceptible animal models.

[REDACTED]

### 3.3 Preclinical Experience with AT-1501

[REDACTED]

[REDACTED]

[REDACTED]

### 3.4 Dose Selection and Rationale

Based on the evidence above, a humanized blocking antibody to CD40LG, AT-1501, was tested in healthy adults and adults with ALS in a randomized, placebo-controlled, double-blind, dose escalation trial. A total of 32 adults; 28 healthy subjects and 4 adults with ALS were enrolled into Cohorts 1-6 (Table 1). Each subject received a single dose AT-1501 or placebo, on Study Day 1, and was followed for safety for 6 weeks (43 days). The primary objective of the study was to determine the safety and tolerability of IV administration of a single dose of AT-1501 in healthy adult volunteers and of one dose in adults with ALS; the secondary objective was to determine the plasma pharmacokinetics of AT-1501 following single ascending doses of AT-1501.

Table 1 AT-1501-101 Dosing Scheme

Cohort	AT-1501 Dose (mg/kg)	Population	No. Active Subjects	No. Placebo Subjects
1	0.5	HS	6	2
2	1.0	HS	3	1
3	1.0	ALS	3	1
4	2.0	HS	3	1
5	4.0	HS	3	1
6	8.0	HS	6	2

HS = Healthy subject

ALS = Subjects with ALS

The doses of AT-1501 administered in the Phase 1 study (0.5, 1, 2, 4, and 8 mg/kg) demonstrated a safety profile comparable to placebo, were well tolerated, and warrant further investigation in adults with ALS. There were no deaths, SAEs, or TEAEs that led to study or study drug discontinuation. There were no clinically significant laboratory results, vital sign assessments, ECG assessments, or physical examination findings. No subject expressed suicidal ideation. Subjects with ALS who were treated with AT-1501 had a similar safety profile as healthy subjects treated with AT-1501 and subjects treated with placebo.

Mean plasma concentrations of AT-1501 increased in a manner that was dose proportional over the dose range tested. The PK parameters in adults with ALS were consistent with those from healthy volunteers at the 1.0 mg/kg dose level. The ADA antibody titers were low. [REDACTED]

PK data from the Phase 1 study were utilized to simulate the steady state exposure in humans receiving an 8.0 mg/kg dose of AT-1501 every 14 days compared to that from the NOAEL dose of 100 mg in the 26-week NHP toxicology study. This results in a mean exposure margin for Cmax and AUC of 17 and 15-fold, respectively, which is appropriate and sufficient to support the therapeutic human doses for this Phase 2a study.

The Phase 2a clinical study will test the safety and tolerability of multiple ascending doses (1.0, 2.0, 4.0, and 8.0 mg/kg) of AT-1501 in adults with ALS [REDACTED]

[REDACTED] Nine participants in each of the lower dose cohorts (1 and 2 mg/kg) will allow for initial review of safety at multiple doses while eighteen participants in the higher cohorts (4 and 8 mg/kg) allows for reduced variability to assess [REDACTED] safety.

## 4 OBJECTIVES OF THE TRIAL

### 4.1 Primary Objective

To determine the safety and tolerability of IV administration of multiple doses of AT-1501 (planned 1.0, 2.0, 4.0 and 8.0 mg/kg).

[REDACTED]

## 5 INVESTIGATIONAL TRIAL DESIGN

### 5.1 Design

[figure not shown]
This is a Phase 2a, multi-center, open label, multiple dose study of AT-1501, a humanized monoclonal antibody antagonist to CD40LG. Approximately 54 adults with ALS will be enrolled into the study in the United States at up to 12 ALS treatment sites in the United States and 1 site in Canada.

Four ascending doses of AT-1501 (1.0 mg/kg; 2.0 mg/kg, 4.0 mg/kg and 8.0 mg/kg) will be administered as a 1-hour IV infusion to sequentially enrolling cohorts. The 1.0 mg/kg and 2.0 mg/kg cohorts will consist of 9 participants each and the 4.0 mg/kg and 8.0 mg/kg cohorts will consist of 18 participants each. The participants in each cohort will receive 6 bi-weekly (every other week) infusions of AT-1501 over an 11-week period.

The primary objective of the study is to assess safety and tolerability.

[REDACTED]

This study consists of a 4-week screening period, an 11-week dosing period in which participants are dosed once every other week, and a 4 week follow-up period. On Day 1 eligible participants will receive their first 1-hour intravenous (IV) infusion of AT-1501 and will be observed for at least 2 hours post infusion before being released. They will return for clinical visits on Weeks 3, 5, 7, 9 and 11 for subsequent infusions and will remain at the clinical site for at least 2 hours for observation and assessments before being released. Participants will be called weekly between dosing visits (Weeks 2, 4, 6, 8, 10 and 12) by a member of the research team to record adverse events (AE) and changes in concomitant medications. Participants will be followed for an additional 4 weeks after their last dose to monitor for safety, with an end of study clinic visit occurring Week 15.

Each participant will be monitored for safety throughout the study. Safety will be assessed by evaluation of AEs, changes in safety laboratory parameters, physical examination including vital signs, ECGs and the Columbia Suicide Severity Rating Scale (C-SSRS).

The dose limiting toxicity observation period to determine the safety of a dose level is defined as starting with administration of the first dose of AT-1501 to the first participant in a cohort through the administration of the second dose of AT-1501 in the 6th participant in that cohort (See 10.3 for Stopping Rules and Dose Limiting Toxicity).

The Data Monitoring Committee (DMC) will meet following the administration of 6 doses to a minimum of 33% of participants, in each cohort to review safety data and to make dose escalation recommendations to Anelixis. The meetings for dosing cohorts 1 and 2 will be held after 3 participants have received 6 doses, for a total of 18 doses. The meetings for dosing cohorts 3 and 4 will be held after 6 participants have received 6 doses, for a total of 36 doses.

## 5.2 Endpoints

[figure not shown]
### 5.2.1 Primary Endpoint

Safety and tolerability variables include incidence of adverse events (AEs), changes in physical examination, vital signs, ECG, laboratory parameters and C-SSRS.

[REDACTED]

### 5.3 Dose Escalation

Participants will be enrolled into 1 of 4 sequentially enrolling cohorts (1.0 mg/kg; 2.0 mg/kg; 4.0 mg/kg; and 8.0 mg/kg). Nine participants will be enrolled into each of the 1.0 mg/kg and 2.0 mg/kg cohorts and 18 participants will be enrolled into each of the 4.0 mg/kg and 8.0 mg/kg cohorts. Dose escalation decisions will be made by Anelixis with input from the DMC (See 5.4 Data Monitoring Committee) and Investigators. After the decision has been made to continue dosing a cohort the next dose cohort will be allowed to start, once the last participant enrolled to the current cohort has received their first dose. This process will be followed for each cohort.

The planned dose escalation scheme may be amended based on review of the emerging data. Additional cohorts may be added, and smaller cohort sizes may be implemented based on safety data and [REDACTED].

## 5.4 Data Monitoring Committee

A DMC will be established and will be comprised of 2 physicians (with ALS experience and no other involvement in the trial) and a statistician.

The committee will meet following the administration of 6 doses to a minimum of 33% of participants, in each cohort. The meetings for dosing cohorts 1 and 2 will be held after 3 participants have received 6 doses, for a total of 18 doses. The meetings for dosing cohorts 3 and 4 will be held after 6 participants have received 6 doses, for a total of 36 doses. The review will include all the available safety and laboratory data, including but not limited to platelet levels and coagulation data. [REDACTED] data may be reviewed depending on data availability. The committee may recommend a revision of the dose escalation scheme based on review of the emerging data.

The DMC is responsible for making a recommendation to continue enrolling at the current concentration, escalate to the next planned dose, recommend changes in study conduct, or stop further dosing in the study. Specific responsibilities of the DMC are detailed in the DMC Charter including meeting schedules, documentation requirements, and data review. The DMC may meet on an ad hoc basis should an emergent safety issue be identified (see [Section 10.3](#)).

## 5.5 Concomitant Therapy

Generally, concomitant medications can be added, changed or discontinued as medically necessary. Appropriate documentation for all forms of pre-medications, supportive care, and concomitant medications will be captured in the source documents. This includes any immunizations or vaccinations received for the duration of the study.

## 5.6 Excluded Medications

The following medications are exclusionary:

- Systemic administration of corticosteroids (PO/IV/IM) at a dose equivalent to 20 mg/day of prednisone for more than 14 consecutive days within 90 days prior to screening,
- Administration of anti-neoplastic and/or immunomodulating agents (e.g. tumor necrosis factor [TNF]  $\alpha$  antagonists or anti-B cell antibodies) or radiotherapy within 1 year prior to screening,
- Cannabinoids unless prescribed or recommended by a physician,
- Any use of experimental therapies,
- Menopausal hormone replacement therapies containing estrogen therapy alone or a combination of estrogen and progesterone agent (E+P),
- Any prior exposure to stem cell and gene therapy (see Section 0 - Exclusion Criteria).

Concomitant medications that are approved drugs or vitamin therapies which the participant may be taking off label are not necessarily exclusionary, recognizing that adults with ALS often take supplemental agents for symptom relief.

#### **5.6.1 Concomitant Use of Radicava® (edaravone) and Rilutek® (riluzole) or Tiglutik (riluzole suspension)**

- Edaravone and riluzole are allowed if the participant has been receiving a stable dose of edaravone for at least 3 months and/or riluzole for at least 1 month prior to Screening.
- Discontinuation of edaravone or riluzole must have occurred at least 3 months for edaravone and 1 month for riluzole prior to Screening for study eligibility.
- The participant and treating physician must anticipate continuing the current treatment regimen with edaravone or riluzole for the duration of the trial.

#### **5.7 Study Duration**

Study enrollment and follow-up may take up to 18 months from first patient first visit to last patient last visit. Each participant will have a study duration of up to 15 weeks from first dosing to the end of study visit. There is a screening period of up to 4 weeks.

### **6 STUDY POPULATION**

Participants will be recruited from neurology practices and through a referral network at facilities treating patients with ALS. Each participating clinical site is evaluated with respect to its ability to enroll the necessary study participants. Strategies for recruitment and retention are discussed during routine monitoring visits. Men and women meeting all the inclusion criteria and none of the exclusion criteria will be allowed to participate.

#### **6.1 Number of Participants**

The number of participants to be enrolled into the study is approximately 54 adults with ALS.

#### **6.2 Participant Screening**

The purpose of Screening Visit 1 is to thoroughly inform, both verbally and in writing, the potential participant about the study and allow him/her the opportunity to ask questions. The potential participant will then sign and date the informed consent form and screening procedures can be performed. Once the consent form is signed the participant is considered enrolled into the study and any serious adverse events that occur will be captured from the date of consent until the end of study participation.

### 6.3 Inclusion Criteria

1. Men and women 18 years or older.
2. ALS diagnosed as possible, laboratory supported probable, probable, or definite as defined by revised El Escorial criteria.
3. ALSFRS-R Aggregate score of 35 or greater, and an aggregate score of 9 or greater at Screening for domains 10 Dyspnea, 11 Orthopnea and 12 Respiratory Insufficiency.
4. No more than 24 months from diagnosis.
5. Women of childbearing potential may be enrolled if a pregnancy test is negative, and they agree to the use of 2 forms of contraception from screening to the end of the study. Males must agree to use 2 forms of contraception from screening to the end of the study if their partners are of childbearing potential.

Acceptable methods of birth control which must be used together are:

- a. Oral contraceptive and condom (combination oral contraceptives containing the second-generation progestin (levonorgestrel) and <30 µg of estrogen should be utilized),
  - b. IUD and condom,
  - c. Diaphragm with spermicide and condom.
  - d. True abstinence is also an acceptable form of birth control
6. No active suicidal ideation with a plan, or behaviors which may be indicative of a participant's intent to complete suicide as determined by the completion of the C-SSRS.
  7. Able and willing to give informed consent, follow trial procedures, and make multiple clinical site visits.

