## 6.6 Study Drug Discontinuation

Participants may be discontinued from receiving study drug for any of the following reasons:

- Lack of cooperation with study requirements;

- Intercurrent illness, that in the opinion of the Investigator, would unreasonably increase the risks of the study procedures, or otherwise compromise the safety of the participant or the integrity of study results;
- Participant refuses further treatment with AT-1501;
- Actions taken to control the -spread of COVID-19 (e.g. no access to study drug)
- Active COVID-19 infection
- Participant Withdraws consent to the trial;
- Stopping rules are met;
- At the direction of Anelixis;
- At the direction of the Investigator.

The effects of AT-1501 have not been studied in patients that have been diagnosed with COVID-19. It is unknown whether taking the investigational drug will increase or decrease the risk of getting COVID-19 or the effect it may have on the clinical course of a participant who develops COVID-19. Potential participants for the study will be tested for COVID-19 prior to entering the study. If a participant tests positive they will not be allowed to participate in the study. If a participant is diagnosed with COVID-19 while receiving treatment in this study, the administration of the investigational drug will be stopped, and appropriate medical care and follow-up will be done. The participant will continue to be monitored for safety.

All participants that withdraw from treatment with AT-1501 for any reason should continue to be followed until the end of study.

If at any time during the study a participant experiences an adverse event the Investigator believes is severe enough to preclude further AT-1501 administration or the stopping rules are met the participant will be discontinued from study drug treatment and will receive medical treatment as determined by the Investigator. The participant will be followed until the event resolves or until the Investigator determines the AE has reached a stable outcome or is no longer clinically significant. Regardless, each participant will be followed for safety for at least 4 weeks from the last AT-1501 infusion. A final visit will be completed according to the end-of-study evaluation (Section 7.6).

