## **10.2 Serious Adverse Events**

### **10.2.1 Definition of a Serious Adverse Event**

A SAE is an adverse event occurring at any dose that results in any of the following outcomes:

- Death
- Life-threatening
- Persistent or significant disability/incapacity
- Prompts a hospital admission or prolongs hospitalization
- Congenital anomaly/birth defect
- Important medical events

Important medical events that may not result in death, be life-threatening, or require hospitalization may be considered serious adverse events when, based upon appropriate medical judgment, they may jeopardize the participant and may require medical or surgical intervention to prevent one of the outcomes listed above. AEs that do not result in any of these outcomes are considered non-serious.

Participants should be closely followed for AEs during the study. Whether or not the adverse events are considered related to the investigational product, they must be reported.

SAEs occurring more than 4 weeks after a patient's last dose of AT-1501 will NOT be reported unless the Investigator feels that the event may have been caused by the investigational product or a protocol procedure.

Pregnancies occurring within the 3-month period after the last treatment, and coming to the attention of the Investigator, should be followed to document any congenital anomalies or birth defects, should they occur. For purposes of consistency, pregnancies will be recorded in the SAE System; however, the event will then be downgraded if the outcome does not meet the SAE criteria.

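### Contraception may stop about 30 days after dose 6, some 61 days before the end of the 3-month period in which known pregnancies are still to be followed

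*Protocol*

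**What the plan says.** Protocol section 6.3, item 5, sets the contraception rule. Women of childbearing potential are eligible if a pregnancy test is negative and "they agree to the use of 2 forms of contraception from screening to the end of the study". For men whose partners could conceive, the rule is "Males must agree to use 2 forms of contraception from screening to the end of the study". The permitted combinations are (a) a low-estrogen combined pill plus condom, (b) an IUD plus condom and (c) a diaphragm with spermicide plus condom; (d) true abstinence is also accepted.

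Section 5.1 describes four weeks of safety follow-up after the last dose, "with an end of study clinic visit occurring Week 15". Appendix A puts that visit at Day 101, plus or minus 7 days, and dose 6 at Day 71, plus or minus 2 days. Section 6.6 adds a floor: "Regardless, each participant will be followed for safety for at least 4 weeks from the last AT-1501 infusion". For those who stop drug early it says: "All participants that withdraw from treatment with AT-1501 for any reason should continue to be followed until the end of study".

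Section 10.2.1 uses two different periods after the last dose. For serious events in general, "SAEs occurring more than 4 weeks after a patient's last dose of AT-1501 will NOT be reported", unless the investigator suspects the product or a protocol procedure. For pregnancy the period is longer: "Pregnancies occurring within the 3-month period after the last treatment, and coming to the attention of the Investigator" are to be followed so that any birth defects are documented.

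**The concern.** The duty to avoid pregnancy ends about one month after the last infusion, while the sponsor's interest in pregnancy outcomes lasts three. Someone who does everything the protocol asks can stop contraception at the Week 15 visit and conceive while section 10.2.1 still wants the outcome followed. No contact is scheduled after that visit, so such a pregnancy is followed only if someone reports it.

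What is at stake is possible fetal exposure to a monoclonal antibody given as six biweekly infusions at up to 8.0 mg/kg. If relevant drug is still present in those two months, a longer contraception period lowers that exposure. If it is not, the extension costs participants some inconvenience and gains nothing. The point concerns participant safety only and has no bearing on the statistical analysis.

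**Working it through.** **Inputs**
- Dose days 1, 15, 29, 43, 57 and 71; every dose after the first has a window of ±2 days (protocol Appendix A; SAP Table 2).
- End-of-study visit: Day 101 ± 7, that is Days 94 to 108 (same sources).
- Minimum follow-up after the last infusion: 4 weeks = 28 days (protocol 6.6).
- Pregnancy follow-up period: 3 months after the last treatment (protocol 10.2.1). I take 91 days as an assumption; three calendar months run from 89 to 92 days.

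**The plan's own figure.** Section 5.1 gives 4 weeks from last dose to end of study. The schedule gives 101 − 71 = 30 days. Week 15 begins on Day 99, and 99 − 71 = 28, so text and schedule agree within the visit window.

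**Dose 6 to the end of the contraception duty**
- Planned: 101 − 71 = 30 days.
- Latest visit, earliest dose: 108 − 69 = 39 days.
- Earliest visit, latest dose: 94 − 73 = 21 days. This breaks the 28-day minimum, so the compliant range is 28 to 39 days.

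**Days left in the 3-month period once contraception may stop (completers)**
- Planned: 91 − 30 = 61 days. With 89 or 92 days for 3 months: 59 or 62.
- Compliant range: 91 − 39 = 52 to 91 − 28 = 63 days.
- Visit windows alone would stretch the upper end to 91 − 21 = 70, but only with follow-up shorter than 6.6 allows.

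**Participants who stop drug early and stay to Day 101, as 6.6 asks**

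| Last dose | Day | Day + 91 | Minus 101 |
|---|---|---|---|
| 1 | 1 | 92 | −9 (no gap) |
| 2 | 15 | 106 | 5 |
| 3 | 29 | 120 | 19 |
| 4 | 43 | 134 | 33 |
| 5 | 57 | 148 | 47 |
| 6 | 71 | 162 | 61 |

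The gap is largest for completers. After dose 1 alone the 3 months end on Day 92, before Day 101. A rule tied only to the last infusion would therefore shorten the present duty for that participant. I give no figure for people who withdraw consent, because their last contact date is not fixed.

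**The case against.** The two provisions do different jobs. Item 5 of 6.3 is a preventive duty. Section 10.2.1 is a rule for pregnancies that the investigator happens to hear about. A capture period longer than the contraception period can be a sensible backstop, and the two need not match. The pharmacological basis for a contraception period would be expected in the preclinical and PK text, much of which is redacted in sections 3.2 to 3.4, or in the Investigator's Brochure. Its absence from the public text therefore cannot be held against the plan.

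There are partial safeguards too. Exclusion 5 bars women expecting to become pregnant, with no stated end date, and footnote 6 of Appendix A puts a urine pregnancy test in the Week 15 safety tests. Lastly, the remedy has a price in this drug class. Section 3.2 refers to thrombotic events with an earlier anti-CD40LG antibody, section 5.6 excludes estrogen-containing menopausal therapy, and exclusion 11 removes people with prior deep venous thrombosis or pulmonary embolism. Two more months on a combined pill, after safety visits have ended and with adherence unchecked, is not free.

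Most of this stands: no contradiction and no missing justification can be claimed. But the safeguards do not close the gap. A Week 15 test says nothing about later conception, and neither safeguard reaches partners of male participants. The estrogen point calls for care in applying the change. Option (c), diaphragm with spermicide and condom, and option (d), abstinence, are already permitted and use no hormones.

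**Conclusion.** The point holds as a precautionary safety improvement. A compliant completer may conceive in about the last 61 days (52 to 63) of the period in which the sponsor still wants known pregnancies followed. That rests on 91 days for 3 months and on reading the end of the study in item 5 as the participant's own Week 15 visit. Section 5.7 supports that reading by measuring each participant's duration to that visit, but item 5 does not define the term.

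Three stronger readings are tempting and unsupported:
- **That 6.3 and 10.2.1 contradict each other.** They do not; one governs behavior and the other follow-up of pregnancies that become known.
- **That the 3 months is the sponsor's view of the risk period.** Nothing in 10.2.1 calls it a washout or risk period. That it is longer than the 4-week limit for other serious events does not make it one.
- **That 30 days is too short.** Exclusion 12 might suggest this, since it requires 30 days or 5 half-lives, whichever is longer, after other investigational agents. Without the half-life or reproductive-toxicity data for AT-1501, the inference cannot be made.

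The expected number of pregnancies cannot be estimated, because the documents do not say how many of the roughly 54 participants could conceive or have partners who could.

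**What to change.** Amend 6.3, item 5, for women and men alike: contraception from screening until the end-of-study visit or 3 months after the last infusion, whichever is later, or another period that the sponsor's PK data support. The later-of wording is needed so that nobody's duty becomes shorter than it is now. At the end-of-study evaluation, give each participant the calendar date on which the period ends, and ask them to report any pregnancy, including a partner's, up to that date. In view of the thromboembolic concern, remind them at the same visit that non-hormonal options are available for the added time.

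The documentary cost is one sentence in 6.3, one instruction at the end-of-study evaluation and matching consent wording. The cost to participants is about two more months of contraception, 52 to 63 days for compliant completers and less for those who stop drug early. For users of option (a) that means two more months of estrogen unless they switch. No visits or tests are added, and no endpoint, analysis or dose-escalation decision changes.
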